7.1.2 Analysis Plan

Outcome change scores (primary endpoints) between time points for each study participant will be calculated. Two-sample T-tests will be conducted first to evaluate whether there is any difference in outcome change scores (with respect to the primary endpoints) between MATCH patients and non-MATCH patients. If differences are observed, the analysis described below will be performed separately for each cohort.

Two-sample T-tests assuming unequal variances will be used for the primary analyses of the change scores between arms. An intention-to-treat approach will be used in which the effect between randomized arms is evaluated, regardless of any treatment crossover. In secondary analyses of the primary endpoints, demographic characteristics between the two arms will be evaluated using T-tests and Fisher's Exact Tests to investigate if the arms were unbalanced with respect to potential confounders. If any potential confounders (in particular age, race/ethnicity and health literacy) are found to have means/proportions that are different between the arms at a p-value of less than 0.1, we will examine the treatment effect in multiple linear regressions of the outcomes in which the randomized arms will be included as a binary (0/1) dummy indicator and all potential confounders that have a p-value < 0.1 will be included as covariates. These analyses will be repeated using the as-treated approach in which we compare differences between the interventions the patient actually received (for example, patients were randomized to the on-line pre-disclosure genetic education but instead received usual care).

There is no plan to perform interim outcome monitoring for this study. Participating patient will be at minimal risk given the nature of the study. The study will be closely monitored for feasibility (Section [7.1.4](#)), and if feasible, information/data gathered would be useful and informative in patient care.

7.1.3 *Exploratory analysis* will be longitudinal changes in cognitive (e.g. genetic knowledge), affective (cancer specific distress, state anxiety, general anxiety and general depression, perceived utility, uncertainty). In these analyses, multiple linear or logistic regressions will be fit to investigate temporal changes in the randomization arm effect, using the Generalized Estimating Equations (GEE) to account for correlated data over time. Unstructured working correlation matrices for GEE will first be considered unless there are model convergence problems, in which case exchangeable working correlation matrices will be used instead. In the regressions, survey wave and the randomized arm will be included as dummy indicator (0/1 variables) covariates. As there are four survey time points, we include three dummy indicators for T1, T2 and T3. In analyzing the change of scores (T1-T0, T2-T0, T3-T0), two dummy indicators will be needed. We will also include interactions between the survey wave indicators and the arm indicator to see if the arm effect changes over time. We will also include potential baseline confounding variables that were not balanced between arms at a p-value < 0.1 (using T-Tests and Fisher's Exact Tests). These analyses will be repeated using the as-treated approach as well.

To evaluate potential moderators as described in Section [2](#), we will add relevant interaction terms to the GEE-estimated multiple linear and logistic regressions described above. Of most interest are interactions between the potential moderators (e.g. test result, sociodemographic factors, health literacy, baseline knowledge or distress) and the arm indicator.

Other exploratory endpoints include satisfaction and regret/disappointment related to tumor genetic test results, and how to better deliver tumor genetic test results and germline information in the future. Summary statistics will be provided and comparison may be explored between arms using T-Tests or Fisher's Exact Tests at two-sided significance level of 0.05.

Rev. 7/17

7.1.4 *Feasibility*

Monitoring enrollment on the primary study:

Accrual will be closely monitored after the addendum expanding eligibility criteria activates. A formal evaluation will start at 6 months after the addendum expanding eligibility criteria activates, allowing some time for the select sites to get ready for enrolling patients. If the rate of enrollment on Step 1 of EAQ152 is < 5 patients per month, the data will be discussed with the study team and the NCI to reevaluate the feasibility of the study.

Monitoring rate of compliance and questionnaire response:

Primary analysis will be based on randomized arms. Patients who have survey data at T0, and at least one of the follow-up timepoints

Rev. 2/17

(T1 or T2), will be considered as evaluable. Among the first 100 patients who are enrolled on Step 1 for the primary study, if proportion of evaluable patients is < 60%, the data will be discussed with the study team and the NCI to re-assess the feasibility. Proportion of patients who cross-over, and proportion of the patients on Arm A who complete the web-based education, will also be reported.

7.2 Secondary Germline Genetic Testing & Counseling Substudy (Step 2 – Arm D and Arm E)

Rev. 7/17

7.2.1 The *primary endpoints* for the substudy will be uptake of remote genetic counseling and uptake of clinical germline testing.

This substudy will be exploratory in nature. We will evaluate, separately, the proportion of individuals who complete a) remote genetic counseling and b) germline testing, among patients (whose hospital sites open accrual to COMET Step 2) with a **potential** clinically significant incidental germline mutation identified through MATCH or non-MATCH tumor profiling. The current COMET Step 2 accrual rate through MATCH is 1-2 patients per month. The substudy will stop patient accrual either when the accrual goal of 100 patients is met or 4 months after the primary study is closed to accrual (allowing the tumor profiling results to be returned back to the sites and so any remaining qualifying patients can be enrolled into the substudy), whichever is earlier.

Rev. 7/17

7.2.2 *Analysis Plan*

The proportions of individual uptake of remote genetic counseling and uptake of clinical germline testing will be calculated separately, along with the 95% confidence intervals.

Changes in knowledge and distress (state anxiety, general anxiety, general depression and cancer specific distress) from baseline to post-pre-test genetic counseling (T0SS to T1SS) and baseline to post-test for those who proceed with confirmatory genetic testing (T0SS to T2SS) will be described using descriptive statistics (e.g. means, standard deviations, proportions, 95% confidence intervals). Multiple linear regressions will be fit to further investigate temporal changes. Again, regression parameters will be estimated using GEE to account for correlated data over time. Unstructured working correlation matrices for GEE will be considered first unless there are model convergence problems, in which case exchangeable working correlation matrices will be used instead. In the regressions, survey wave as dummy indicator (0/1 variables) will be included as covariates. As there are three survey time points, we include two dummy indicators for T1 and T2 (leaving T0 as the baseline reference time period). We will also include potential baseline confounding variables in the models (e.g. age, sociodemographic variables).

Other exploratory endpoints include communication to others, satisfaction and regret/disappointment related to genetic counseling service or germline genetic test results. Summary statistics will be provided.

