As MATCH has approached its goal of sequencing ~6000 patient tumors, this section incorporates changes to expand eligibility criteria (effective since Addendum #3) to allow patients from select sites who potentially undergo tumor profiling through non-MATCH assays and to increase the accrual goal (effective since Addendum #6). In this section, patients who enter COMET through MATCH Step 0 (prior to or after the activation of this addendum allowing for eligibility expansion) will be referred as the MATCH cohort, and other patients (who enter after the corresponding addendum activates) will be referred as the non-MATCH cohort.

7.1 Primary Study: Randomized Study of Web-based Pre-disclosure Genetic Education versus Usual Care (Step 1 – Arms A & B)

Rev. 2/17

NOTE: Patients on Arm C (see Section [□□□□](#)) will not participate in or complete any primary study (Step 1) education or surveys, and will immediately be registered to Arm E and complete all of the substudy (Step 2) procedures.

Rev. 7/17

7.1.1 *Primary endpoints* will include change in knowledge and distress (state anxiety, Promis anxiety, Promis depression and cancer specific distress) from baseline to post-education (T0 to T1) and baseline to post-disclosure (T0 to T2).

The following 10 analyses are of primary interest: change scores from T0 to T1, and T0 to T2 of each of the following five outcomes: knowledge, state anxiety, cancer specific distress, Promis anxiety and Promis depression, which correspond to 10 primary analyses. To account for the 10 primary analyses, A Bonferroni correction is considered here, setting the nominal p-value to declare statistical significance of $p < 0.005$ (5% Typical Type I error rate / 10 comparisons = 0.5% nominal p-value for declaring statistical significance). Preliminary data from the COMET pilot study (State Anxiety, IES-Total, Knowledge) is used to calculate power. As there was no preliminary data for Promis Depression/Anxiety in a similar setting, power calculation for these two measurements are based on data reported in Hinds et al. (2012). A sample size of 200 (with evaluable paired data) /arm is chosen here, which provides at least 85% power for all short-term outcomes (e.g. T0-T1) and changes in knowledge and cancer specific distress after receipt of tumor profiling results (e.g. T0-T2), using t test at two-sided 0.005 significance level.

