With the completion rate for both T0 and T1 surveys at approximately 60% (as analyzed in May 2018) and the goal of evaluable sample size at 200/arm (at least for the analysis of changes between T0 and T1), the accrual goal of the primary intervention study needs to be inflated from 400 to 670 patients in order to maintain sufficient power for detecting proposed changes from T0 to T1 and changes in knowledge and cancer specific from T0 to T2 (as described in the preceding paragraph). With the completion rate for both T0 and T2 surveys at approximately 45% (as analyzed in May 2018), the projected evaluable sample size of 150 patients/arm can give the power of 72% for changes in knowledge and 95% for changes in cancer specific distress from T0 to T2. These 670 patients will be randomized 1:1 between the two arms, and the randomization will be stratified by gender, race, age (> 65 vs. ≤ 65), and education level. As of this analysis time, 320 patients have been enrolled into the primary intervention study. The current COMET accrual rate is approximately 15 patients per month (based on the last 3 months). Assuming 15, 20 or 25 patients per month (as more expansion sites are added over time) can be accrued to COMET from the select sites, it is expected to take 23, 17 or 14 additional months, respectively, to complete Step 1 accrual of 670 patients.

The original accrual plan posed a limitation on White patients at 80% of the accrual goal to ensure diversity of patients. Given that the accrual of this study might terminate early if the funding of this study ends, the accrual limitation on White patients is being lifted to ensure the maximal number of patients enrolled before funding ends.

Power for various sample sizes

Variable	Change score time period	Sample Size Per Arm	Power for p< 0.005, 2-sided	Change Score Group 1	Change Score Group 2	Standard Deviation Group 1	Standard Deviation Group 2
State Anxiety	T0 to T1	100	98%	2.71	-2.78	8.24	7.43
State Anxiety	T0 to T1	150	100%	2.71	-2.78	8.24	7.43
State Anxiety	T0 to T1	200	100%	2.71	-2.78	8.24	7.43
State Anxiety	T0 to T1	300	100%	2.71	-2.78	8.24	7.43
State Anxiety	T0 to T1	400	100%	2.71	-2.78	8.24	7.43
State Anxiety	T0 to T1	61	85%	2.71	-2.78	8.24	7.43
IES-Total	T0 to T1	100	100%	0.29	-1.78	1.70	3.19
IES-Total	T0 to T1	150	100%	0.29	-1.78	1.70	3.19
IES-Total	T0 to T1	200	100%	0.29	-1.78	1.70	3.19
IES-Total	T0 to T1	300	100%	0.29	-1.78	1.70	3.19
IES-Total	T0 to T1	400	100%	0.29	-1.78	1.70	3.19

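### An undefined pretest of MATCH versus non-MATCH mean change decides whether the primary arm comparison is split by cohort; it does not test the education effect, and alpha and power are set only for the unsplit analysis

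*Combined protocol and SAP*

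**What the plan says.** Section 7.1.2 of the combined protocol and SAP puts a preliminary step before the primary analysis. Two-sample t-tests are run to "evaluate whether there is any difference in outcome change scores (with respect to the primary endpoints) between MATCH patients and non-MATCH patients". The consequence follows at once: "If differences are observed, the analysis described below will be performed separately for each cohort". The analysis that comes below that sentence includes the primary one: "Two-sample T-tests assuming unequal variances will be used for the primary analyses of the change scores between arms".

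The error rate and sample size are in section 7.1.1. There are ten primary analyses, five outcomes at each of T0–T1 and T0–T2: "To account for the 10 primary analyses, A Bonferroni correction is considered here", giving 0.005 per test. Power is computed on total evaluable patients per arm: 200 as the design target, and for T0–T2 a "projected evaluable sample size of 150 patients/arm can give the power of 72% for changes in knowledge" and 95% for cancer-specific distress. No cohort size, within-cohort power or alpha for a split analysis is given.

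Cohort does not appear elsewhere in the planned comparisons. In 7.1.1, "the randomization will be stratified by gender, race, age" and education level, not by cohort. In 7.1.3 the moderator analyses are described as follows: "Of most interest are interactions between the potential moderators (e.g. test result, sociodemographic factors, health literacy, baseline knowledge or distress) and the arm indicator". That list is open, but cohort is not among its examples.

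**The concern.** The pretest compares the wrong things. A difference in average change between MATCH and non-MATCH patients is a cohort main effect. It does not bias a pooled comparison of arms randomized 1:1, and it does not show that education works differently in the two cohorts. That question needs an arm-by-cohort interaction. The rule can therefore split the analysis when pooling is sound, and leave it pooled when the effects differ.

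The rule is also not fully defined. No significance level is attached to it. The 0.1 level in 7.1.2 is for baseline imbalance between arms, and the 0.05 level in 7.1.3 is for other exploratory endpoints. Nor is it clear whether one differing outcome splits all ten analyses or just that one. Two analysts could follow the text correctly and report different primary results.

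At stake are the study-wide error rate, which was set for ten tests, and the power of the comparisons with least to spare.

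**Working it through.** **Inputs.** From 7.1.1: two-sided 0.005 per test; accrual 670; completion 60% for T0–T1 and 45% for T0–T2; tabled means and SDs. Assumed, because the documents do not give them: the cohort mix (320/350, and 200/470 as a more uneven case), the pretest level (0.05 or 0.005), and the split rule. The 320 is the number already enrolled at the re-sizing analysis, which 7.1.1 does not break down by cohort.

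**1. Reproduce the stated figures.** Alpha: 0.05/10 = 0.005. Power (normal approximation) = Φ(Δ/SE − 2.807), with SE = √((s₁² + s₂²)/n).
- T0–T2 knowledge, n = 150 per arm: Δ = 5.86 − 4.40 = 1.46; SE = √((4.30² + 3.05²)/150) = 0.430; ratio 3.39; power 72% (stated 72%).
- T0–T2 IES-Total, n = 150: Δ = 1.17; SE = √((1.53² + 2.86²)/150) = 0.265; ratio 4.42; power 95% (stated 95%).

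**2. Power after a split.** Evaluable per arm = cohort × completion / 2. At 320/350 this is 96 and 105 for T0–T1, and 72 and 79 for T0–T2. At 200/470 it is 60 and 141, and 45 and 106.

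| Outcome | Pooled | 320/350 | 200/470 |
|---|---|---|---|
| Knowledge T0–T2 | 72% | 32% / 36% | 17% / 52% |
| IES-Total T0–T2 | 95% | 60% / 65% | 35% / 82% |
| PROMIS T0–T1, 0.33 SD | 69% recomputed (91% stated) | 30% / 34% | 16% / 49% |

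T0–T1 state anxiety, IES-Total and knowledge keep 96% or more at 320/350. At 200/470 the smaller cohort has 85%, 95% and 80%. The pooled PROMIS figure does not reproduce at 0.005, and neither does the stated power for T0–T2 state anxiety, which is left out. Both are separate matters.

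**3. Number of tests.** Splitting one to ten outcomes gives 11 to 20 tests. The bound for a full split is 20 × 0.005 = 0.10; if the tests are independent, 1 − 0.995²⁰ = 0.095.

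**4. Chance of a split with no cohort difference.** For ten independent pretests, 1 − 0.95¹⁰ = 40% at 0.05 and 1 − 0.995¹⁰ = 4.9% at 0.005.

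**5. What the pretest responds to.** One outcome, SD 1, 96 and 105 per arm (cohort totals 192 and 210), 20,000 simulated trials.
- *Same 0.33 SD effect in both cohorts, 0.3 SD cohort shift.* The pretest splits 84% of the time at 0.05 and 55% at 0.005. Check: SE = √(1.027 × (1/192 + 1/210)) = 0.101; 0.3/0.101 = 2.96; Φ(2.96 − 1.96) = 84%.
- *Same shift, no arm effect.* The pooled Welch test rejects 0.46% of the time at a nominal 0.5%, so the split protects nothing.
- *0.66 SD effect in one cohort only, equal cohort means.* The pretest at 0.05 splits 4% of the time; an interaction test at 0.05 detects the difference 91% of the time. Check: SE = √(2/96 + 2/105) = 0.200; 0.66/0.200 = 3.30; Φ(3.30 − 1.96) = 91%.
- *Same one-cohort effect, equal control means.* The cohort mean moves by 0.33 SD and the pretest at 0.05 splits 90% of the time.

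**6. Family-wise error of the two-stage procedure, no arm effect.** Simulated at 320/350 with ten outcomes, independent unless stated.
- No cohort difference: 4.9% to 6.8%, depending on pretest level and split rule (400,000 runs).
- 0.3 SD shift on all ten outcomes, 60% completion throughout (300,000 runs): 9.5% if all split; 9.0% (pretest at 0.05) or 7.6% (0.005) if only the differing outcome splits.
- The same with outcome correlation 0.5: 7.4–7.5% if all split, and 6.2–7.1% if only the differing outcome splits.

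**The case against.** The best defence is that the pretest does not look at arm. It does not select on the treatment effect: each within-cohort test keeps its 0.005 level given a split, the pooled test keeps its level given no split, and within-cohort comparisons remain randomized and unbiased. The inflation comes only from the number of tests, and it is small unless the cohorts really differ. Nothing in the documents supports a 0.3 SD shift. With a 0.1 SD shift and only the differing outcome split, the error is 5.0–5.6%; with 0.2 SD it is 5.7–7.1%. Using 45% completion for the T0–T2 outcomes lowers the 9.0% and 7.6% figures to about 8.6–8.7% and 7.0–7.2%, and the 84% and 55% trigger rates to about 73% and 40% for those outcomes. The example in which the pretest misses heterogeneity needs control means that exactly offset the effect. There is also a reason to look at cohorts separately: usual care in section 5.2.1 can include contact with MATCH research staff. Finally, stating a level and a split rule and testing at 0.0025 after a split would also control error.

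All of this stands, and it limits the harm to cases where a split occurs. It does not rescue the rule. The plan has no provision for a split, its pretest picks up heterogeneity only incidentally, and testing at 0.0025 would lower power further: T0–T2 knowledge to about 25% and 29% at 320/350. An interest in cohort differences is better served by an interaction test.

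**Conclusion.** The concern holds. As written, the form of the primary analysis depends on a test of the wrong quantity, with no level and no split rule. Following the text can produce up to 20 tests at a level set for 10, with a bound of 10% instead of 5%, and it removes the power basis given in 7.1.1. The clearest loss is T0–T2 knowledge, from 72% to 32% and 36% at an assumed 320/350 mix, or 17% and 52% at 200/470. Three T0–T1 outcomes (state anxiety, IES-Total and knowledge) are little affected at an even mix.

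The criticism of what the pretest measures, and of its missing level and split rule, needs no assumption. The sizes do: they depend on cohort mix, pretest level, split rule, true cohort difference and correlation between outcomes, none of which the documents give. If cohort means do not differ, overall error stays between 4.9% and 6.8%. Because all ten primary analyses are affected, this should be settled before outcome data are examined.

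**What to change.** Delete the preliminary cohort t-tests and the instruction to split. State that the pooled Welch t-test of change scores between randomized arms, at 0.005, is the primary analysis in all cases. Add three secondary analyses:

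1. a regression of change score on arm, adjusted for cohort, with robust (unequal-variance) standard errors;
2. a test of the arm-by-cohort interaction;
3. arm differences within each cohort with confidence intervals, reported descriptively and without significance claims.

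This costs only analysis-plan wording. The primary test, its level, the sample size and the data collected stay as planned, and the interaction test directly addresses whether the education effect differs between MATCH and non-MATCH patients.

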4.1.3 Classification and Stratification Factors

4.1.3.1 Classification Factors:

- Primary Study (RCT) Participation: Yes vs. No.

4.1.3.2 Stratification Factors:

- Gender: Male vs. Female
- Race: White vs. Others
- Age: ≤ 65 vs. > 65 years
- Education level: No college vs. College vs. Professional/Graduate

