IES-Total	T0 to T1	46	85%	0.29	-1.78	1.70	3.19
Knowledge	T0 to T1	100	97%	1.70	-1.50	6.11	3.02
Knowledge	T0 to T1	150	100%	1.70	-1.50	6.11	3.02
Knowledge	T0 to T1	200	100%	1.70	-1.50	6.11	3.02
Knowledge	T0 to T1	300	100%	1.70	-1.50	6.11	3.02
Knowledge	T0 to T1	400	100%	1.70	-1.50	6.11	3.02
Knowledge	T0 to T1	68	85%	1.70	-1.50	6.11	3.02
State Anxiety	T0 to T2	100	13%	-2.43	5.00	4.04	14.58
State Anxiety	T0 to T2	150	23%	-2.43	5.00	4.04	14.58
State Anxiety	T0 to T2	200	34%	-2.43	5.00	4.04	14.58
State Anxiety	T0 to T2	300	55%	-2.43	5.00	4.04	14.58
State Anxiety	T0 to T2	400	72%	-2.43	5.00	4.04	14.58
State Anxiety	T0 to T2	512	85%	-2.43	5.00	4.04	14.58
IES-Total	T0 to T2	100	79%	-1.00	-2.17	1.53	2.86
IES-Total	T0 to T2	150	95%	-1.00	-2.17	1.53	2.86
IES-Total	T0 to T2	200	99%	-1.00	-2.17	1.53	2.86
IES-Total	T0 to T2	300	100%	-1.00	-2.17	1.53	2.86
IES-Total	T0 to T2	400	100%	-1.00	-2.17	1.53	2.86
IES-Total	T0 to T2	114	85%	-1.00	-2.17	1.53	2.86
Knowledge	T0 to T2	100	48%	5.86	4.40	4.30	3.05
Knowledge	T0 to T2	150	72%	5.86	4.40	4.30	3.05
Knowledge	T0 to T2	200	86%	5.86	4.40	4.30	3.05
Knowledge	T0 to T2	300	98%	5.86	4.40	4.30	3.05
Knowledge	T0 to T2	400	100%	5.86	4.40	4.30	3.05
Knowledge	T0 to T2	194	85%	5.86	4.40	4.30	3.05

Power for Promis Depression and Promis Anxiety

With 200 evaluable patients per arm, there is 91% power to detect an effect size of 0.33 (as fraction of standard deviation), using t-test at two-sided significance level 0.005. Based on data from 92 children/adolescents, Hinds et al. (2012) reported standard deviation of 10.74 for Promis Depression and 12.5 for Promis Anxiety, respectively. Assuming the standard deviations for these two measurements in our proposed study are similar, the following table gives the absolute difference that can be detected with 91% power, under different assumptions for the correlation between the measurements across two timepoints, at two-sided significance level 0.005.

Variable	Correlation	Standard deviation of change	Effect size (as fraction of standard deviation)	Absolute difference	Power
Promis Depression	0.4	11.8	0.33	3.89	91%
Promis Depression	0.6	9.6	0.33	3.17	91%
Promis Depression	0.8	6.8	0.33	2.24	91%
Promis Anxiety	0.4	13.7	0.33	4.5	91%
Promis Anxiety	0.6	11.2	0.33	3.7	91%
Promis Anxiety	0.8	7.9	0.33	2.6	91%

Rev. 7/17

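### The primary t-test on change scores leaves out the baseline score and the randomization strata; for PROMIS, at the plan's correlations and equal SDs, it needs 43/25/11% more patients than ANCOVA

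*Combined protocol and SAP*

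**What the plan says.** Section 7.1.1 defines ten primary analyses: changes from T0 to T1 and from T0 to T2 in knowledge, state anxiety, cancer-specific distress, PROMIS anxiety and PROMIS depression. Each is tested at two-sided 0.005 (Bonferroni). Section 7.1.2 gives the method: "Two-sample T-tests assuming unequal variances will be used for the primary analyses of the change scores between arms".

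Section 7.1.1 also says that "the randomization will be stratified by gender, race, age" and education. Section 4.1.3.2 lists the levels, for example "Education level: No college vs. College vs. Professional/Graduate". None of these factors is in the primary test.

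Covariates appear only later. The secondary regressions in 7.1.2 include variables that "are found to have means/proportions that are different between the arms at a p-value of less than 0.1"; age, race/ethnicity and health literacy are singled out, the T0 outcome score is not. The exploratory GEE models in 7.1.3 add "potential baseline confounding variables that were not balanced between arms at a p-value < 0.1". The moderator models in 7.1.3 bring in baseline knowledge or distress as interactions with arm without that filter, but they too are exploratory.

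On power, 7.1.1 says of PROMIS: "With 200 evaluable patients per arm, there is 91% power to detect an effect size of 0.33" SD at two-sided 0.005. It tabulates detectable differences "under different assumptions for the correlation between the measurements across two timepoints". For T0 to T2, the projected 150 patients per arm "can give the power of 72% for changes in knowledge".

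**The concern.** A change score is follow-up minus T0, that is, a baseline adjustment with the slope fixed at 1. The slope that minimizes the residual variance is r × (SD at follow-up / SD at T0). Unless that product equals 1, the change score carries avoidable noise. The strata were thought important enough to balance at randomization, yet whatever outcome variation they explain is left in the error term.

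This matters where power is short, as it is for PROMIS and for T0–T2 knowledge. It matters little for the pilot-based T0–T1 outcomes (stated 100% at 200 per arm) and for T0–T2 cancer-specific distress (stated 95% at 150 per arm). Section 7.1.1 had to raise accrual from 400 to 670 because of survey non-completion and warns that accrual could stop early if funding ends. Getting more information from each evaluable patient is a remedy that does not depend on accrual.

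The p < 0.1 rule does not fill the gap. It selects covariates on chance imbalance rather than on how strongly they predict the outcome, and it leaves the adjusted model unknown until the data are seen. Stratified randomization also makes imbalance in the strata less likely, so the rule will tend to leave out the factors the design treated as important. It does not touch the primary inference.

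**Working it through.** **Inputs (Section 7.1.1).** PROMIS SD 10.74 (depression) and 12.5 (anxiety); correlation r = 0.4, 0.6, 0.8; effect 0.33 SD of change; two-sided alpha 0.005 (critical value 2.807); 200 evaluable per arm for T0–T1. For T0–T2, 670 × 0.45 / 2 = 151 per arm, which the plan gives as 150.

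**Step 1: the plan's SDs of change.** With equal SDs at both times, SD of change = SD × √(2(1 − r)).

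| r | Depression, computed (stated) | Anxiety, computed (stated) |
|---|---|---|
| 0.4 | 11.77 (11.8) | 13.69 (13.7) |
| 0.6 | 9.61 (9.6) | 11.18 (11.2) |
| 0.8 | 6.79 (6.8) | 7.91 (7.9) |

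The table reproduces, so equal SDs are the plan's own assumption for PROMIS.

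**Step 2: the plan's PROMIS power.** Power = Φ(0.33 × √(200/2) − 2.807) = Φ(0.493) = 69% (68% by noncentral t). The stated 91% does not reproduce at 0.005. With critical value 1.960 (alpha 0.05), Φ(3.30 − 1.960) = 91.0%. That is a separate discrepancy; it does not affect Step 3, which involves neither alpha nor effect size.

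**Step 3: efficiency of ANCOVA against the change score.** Let k = SD at follow-up / SD at T0, in units of the T0 SD.

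- Var(change) = 1 + k² − 2rk
- Var(ANCOVA residual) = k²(1 − r²)
- At k = 1 the ratio ANCOVA/change is (1 − r²) / (2(1 − r)) = (1 + r)/2

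The extra patients needed by the change score are 1/ratio − 1. PROMIS power with adjustment is Φ(0.33/√ratio × √(n/2) − 2.807).

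| r (k = 1) | Ratio | Extra patients | Power, 200/arm | Power, 150/arm |
|---|---|---|---|---|
| change score | 1 | – | 69% | 52% |
| 0.4 | 0.70 | 43% | 87% | 73% |
| 0.6 | 0.80 | 25% | 81% | 65% |
| 0.8 | 0.90 | 11% | 75% | 58% |

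The 150-per-arm column assumes the same 0.33 SD at T2. Noncentral t gives values within one point. Because 0.33 is a fraction of the SD of change, the rows refer to different absolute differences (for depression, 3.89 at r = 0.4 and 2.24 at r = 0.8). Each row should be compared with the change score at the same r, not with the other rows.

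**Step 4: sensitivity to equal SDs.** The range for k is an assumption.

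| k | Extra patients at r = 0.4 / 0.6 / 0.8 |
|---|---|
| 0.8 | 86% / 66% / 56% |
| 1 | 43% / 25% / 11% |
| 1.25 | 19% / 6% / 0% |

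At k = 1.25 and r = 0.8 the slope is 0.8 × 1.25 = 1, so the two analyses coincide. At k = 1.25, power at 200 per arm is 79%, 72% and 69%.

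**Step 5: T0–T2 knowledge, illustration only.** The documents give no correlation or T0 SD for knowledge. From the power table, d = (5.86 − 4.40) / √((4.30² + 3.05²)/2) = 0.392. At 150 per arm, power is Φ(0.392 × √75 − 2.807) = 72%, as stated. Borrowing the PROMIS correlations with k = 1 gives 89%, 84% and 78%; with k = 1.25 it gives 81%, 75% and 72%.

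**The case against.** The strongest reply is that nothing here is wrong: a pre-specified Welch test on change matches an endpoint defined as change, and no conclusion would be invalid. That is so, and it is why this is a recommended improvement and not an error.

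The second reply is that 43/25/11% depends on equal SDs and on correlations that the plan assumes rather than estimates, set beside SDs from 92 children and adolescents. This also stands. At an SD ratio of 1.25 the gain is small for r = 0.6 and nil for r = 0.8. But the gain does not turn negative: in large samples with 1:1 allocation, ANCOVA is not less efficient than the change score.

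Three narrower points stand as limits.

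- The knowledge figures are only an illustration. With equal SDs, the arms' different SDs of change (4.30 and 3.05) would imply different correlations by arm.
- The lowest stated power is for T0–T2 state anxiety (23% at 150 per arm). Those rows reproduce only with a difference of 5.00 − 2.43 = 2.57, not the tabulated −2.43 versus 5.00 (a gap of 7.43). No correlation is given either, so the benefit there cannot be judged.
- T0 is completed after registration, and patients without it go off study (Section 4.3), so randomization does not guarantee T0 balance among the evaluable. Where balance fails, the two analyses can give different estimates. T0 does precede Arm A's access to the website (Section 5.2.1), so it remains a legitimate baseline covariate, and the change score relies on the same T0 value.

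**Conclusion.** The concern holds. The primary analysis gives up precision that the trial could have without collecting anything more. For PROMIS, on the plan's own correlations and equal SDs, the change score needs 43%, 25% or 11% more evaluable patients than a T0-adjusted model; for SD ratios of 0.8 to 1.25 the range is 86% down to 0%. At the plan's alpha, that is the difference between 69% power and 75–87% at 200 per arm, and between 52% and 58–73% at 150 per arm (equal SDs, 0.33 SD of change, MATCH and non-MATCH patients analysed together). These figures cover T0 adjustment only. The gain from the strata, and the gain for knowledge, state anxiety and cancer-specific distress, cannot be computed from the documents. The Welch test remains valid, so this is a change the team should make, not one the trial's validity depends on.

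**What to change.** For each of the ten primary analyses, pre-specify a linear regression of the follow-up score (or, equivalently for the arm effect, the change score) on arm, the T0 value of that outcome and the four stratification factors. Use heteroscedasticity-robust standard errors to keep the allowance for unequal variances. Retain the Welch test on change scores as a sensitivity analysis. In 7.1.2 and 7.1.3, replace selection on imbalance at p < 0.1 with a fixed covariate list, adding health literacy if wanted.

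The cost is an analysis-plan amendment made before outcomes are compared by arm; Section 7.1.2 plans no interim outcome monitoring. The strata are recorded at registration, and Section 7.1.4 already requires T0 for a patient to be evaluable. The model uses 6 covariate degrees of freedom (T0 1, gender 1, race 1, age 1, education 2) against about 300 to 400 evaluable patients. The sample size can stay. The change-score power table can be kept as a conservative basis, since the documents give no T0 SDs or correlations for re-powering the pilot-based outcomes, but the PROMIS 91% needs its own correction.
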